TITLE: A comparison of Oral VTS-K (combination of VTS-Aspirin and oral ketamine) to Nurtec (Rimegepant) for managing acute headache in the ED: randomized, open-label, clinical trial.

NCT#:

Document Date: March 23, 2021

TITLE: A comparison of Oral VTS-K (combination of VTS-Aspirin and oral ketamine) to Nurtec (Rimegepant) for managing acute headache in the ED: randomized, open-label, clinical trial.

INTRODUCTION

Headaches affect over 50% of patients annually, with close to 4% of ED visits for headache. Most headaches managed in the ED are benign, with 90% of these headaches classified as tension, migraine, or cluster. At present, the satisfaction with ED treatment of headache is low, and despite the multitude of available medications, the evidence- based treatment options are often quite limited. There are over twenty different types of medications available to the ED clinicians for managing headache, many with different routes of administration (parenteral, intranasal, subcutaneous, and oral). Many of these medications are provided in so-called “headache cocktail”, which varies based on the physician, institution, and patient preferences.

STUDY OBJECTIVES

To compare analgesic efficacy and rates of side effects of a proprietary formulation of orally administered aspirin and ketamine (AOK) to a Nurtec ODT (Rimegepant) for pain management in adult ED patients presenting to the ED with acute headache.

HYPOTHESIS

We hypothesize that the administration of AOK will provide similar analgesia at 60 minutes post-administration in comparison to Nurtec (Rimegepant) in adult patients presenting to the ED with acute headache. The primary outcome of this trial is the difference in participant’s pain scores at 60 minutes post-medication administration.

STUDY DESIGN

Subjects: Patients 18 years of age and older presenting to the ED with acute headache (defined as HA lasting no more than 1 week) and an initial pain score of 5 or more on a standard 11- point (0 to 10) numeric rating scale and requiring oral analgesia as determined by the treating attending physician. Patients’ screening and enrollment will be performed by study investigators and research assistants. All patients will be enrolled at various times of the day when study investigators will be available for patient enrollment and an ED pharmacist will be available for medication preparation.

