Eligibility Criteria: Patients 18 years of age and older presenting to the ED with acute headache (<7 days) and an initial pain score of 5 on a standard 11-point (0 to 10) numeric rating scale. Patients will have to be awake, alert, and oriented to person, place, and time, and will be able to demonstrate understanding of the informed consent process and content. Patients also will have to demonstrate ability to verbalize the nature of any adverse effects they might experience as well as to express their pain severity by using the NRS.

Exclusion Criteria: Patients with altered mental status, allergy to aspirin, ketamine, rimegepant, pregnant patients, unstable vital signs (systolic blood pressure <90 or >180 mm Hg, pulse rate <50 or >150 beats/min, and respiration rate <10 or >30 breaths/min), inability to provide consent, consumption of Aspirin/NSAID's within 6 hours of arrival to the ED, or acetaminophen within 4 hours of arrival to the ED, active PUD, history of GI Hemorrhage, history of renal and hepatic insufficiency, past medical history of alcohol or drug abuse, or schizophrenia, as well as clinical findings concerning for acute intracranial process, acute infections process, or vascular catastrophe, pregnant patients and breastfeeding patients.

Design: This is a prospective, randomized, open-label, equivalence trial comparing analgesic efficacy and safety of AOK and Nurtec (Rimegepant) in patients presenting to the ED of Maimonides Medical Center with acute headache. Upon meeting the eligibility criteria, patients will be randomized into one of the two study arms: Group I will receive AOK, and Group II will receive Nurtec

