Expected Outcomes: The primary outcome will include a comparative reduction of pain scores on numeric rating pain scale (NRS) at 60 minutes from the baseline. The secondary outcomes will include a need for rescue analgesia, rates of adverse effects, and change in pain score up to 120 minutes.

Adverse Events:

With respect to unique adverse effects of ketamine, we will use Side Effect Rating Scale for Dissociative Anesthetics (SERSDA) and Richmond Agitation Sedation Scale (RASS) (ref) SERSDA Scale includes fatigue, dizziness, nausea, headache, feeling of unreality, changes in hearing, mood change, general discomfort, and hallucinations with severity of each graded by patients on a five-point scale, with “0” representing the absence of any adverse effects and “4” representing a severely bothersome side effect. RASS evaluates the severity of agitation and/or sedation in accordance with the nine-point scale with scores ranging from “-4” (deeply sedated) to “0” (alert and calm) to “+4” (combative).

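### Side-effect rates are to be compared between arms, but the only named instruments are introduced for ketamine, with no statement that both arms complete them and no common prompt for other effects

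*Combined protocol and SAP*

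**What the plan says.** The between-arm safety comparison appears three times. The Study Objectives section sets it beside efficacy: "To compare analgesic efficacy and rates of side effects of a proprietary formulation of orally administered aspirin and ketamine (AOK") against rimegepant. The Design paragraph calls the study a "randomized, open-label, equivalence trial comparing analgesic efficacy and safety of AOK and Nurtec (Rimegepant"). Expected Outcomes lists it again: "The secondary outcomes will include a need for rescue analgesia, rates of adverse effects, and change in pain score up to 120 minutes".

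On measurement, the Adverse Events section offers two scales and one reason for choosing them: "With respect to unique adverse effects of ketamine, we will use Side Effect Rating Scale for Dissociative Anesthetics (SERSDA) and Richmond Agitation Sedation Scale (RASS"). It describes their content as follows:

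- "SERSDA Scale includes fatigue, dizziness, nausea, headache, feeling of unreality, changes in hearing, mood change, general discomfort, and hallucinations", each graded by the patient from 0 to 4.
- "RASS evaluates the severity of agitation and/or sedation in accordance with the nine-point scale".

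No assessment times are given for either scale, and neither is assigned to one arm or to both. The data-sheet contents listed under Data Collection Procedures include no adverse-effect item, although that list is not presented as complete. The only other mention of adverse effects is an eligibility condition that the patient can describe them, which is not a collection procedure.

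**The concern.** A comparison of side-effect rates is interpretable only if both arms are asked the same questions in the same way at the same times. Here the instruments are justified by a component of one arm. The plan neither says that the other arm is scored nor names an instrument for effects of aspirin or rimegepant. In an open-label trial, whoever asks about symptoms knows which drug was given, so any discretion over what to ask, and of whom, can follow the allocation.

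The plan recognises risks that the scales do not cover. Its exclusions include "active PUD, history of GI Hemorrhage, history of renal and hepatic insufficiency" and allergy to any of the three study drugs, yet neither scale, as described, asks about bleeding, abdominal pain, vomiting or rash.

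At stake is a secondary outcome that forms half of the objective. The primary pain comparison is not affected. Uneven ascertainment cannot be repaired once the data have been collected.

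**Working it through.** **Plan's own figure.** The plan gives no sample size or power for adverse effects, so there is nothing to reproduce on this point. The only number borrowed from Sample Size is the planned enrolment of 45 per group.

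**What each reading of the Adverse Events section would capture**

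| Type of effect | Both arms scored | Group I only scored |
|---|---|---|
| Dissociative and sedative (unreality, hearing, mood, hallucinations; RASS) | Prompted equally | Prompted in AOK only |
| General (fatigue, dizziness, nausea, headache, discomfort) | Prompted equally | Prompted in AOK only |
| Bleeding, abdominal pain, vomiting, rash | No named prompt in either arm | No named prompt in either arm |

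Five of the nine SERSDA items (fatigue is the arguable one) are general symptoms, asked about whichever drug caused them. With both arms scored, the remaining gap is the last row. With Group I only scored, the first two rows are uneven as well.

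**Illustration of the Group I-only reading.** The plan supplies none of the symptom or capture rates below; all are assumptions. Let the true rate be p in both arms, with prompting finding every case and no prompting finding a fraction c. The observed rates are then p in Group I and p × c in Group II, and the spurious difference is p(1 − c). The chance of p<0.05 uses the two-sided normal approximation with n = 45 per arm:

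Φ[(d − 1.96·SE0)/SE1], where SE0 = √[2·p̄(1−p̄)/n] and SE1 = √{[p1(1−p1) + p2(1−p2)]/n}.

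Worked case, p = 0.30 and c = 0.5:

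- p1 = 0.30, p2 = 0.15, d = 0.15, p̄ = 0.225.
- SE0 = √(2 × 0.225 × 0.775/45) = 0.088.
- SE1 = √[(0.21 + 0.1275)/45] = 0.087.
- Φ[(0.15 − 1.96 × 0.088)/0.087] = Φ(−0.26) = 0.40.

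| True rate, both arms | Unprompted capture | Recorded, AOK vs rimegepant | Spurious difference (points) | Chance of p<0.05 |
|---|---|---|---|---|
| 20% | 75% to 25% | 20% vs 15% to 5% | 5 to 15 | 9% to 58% |
| 30% | 75% to 25% | 30% vs 22.5% to 7.5% | 7.5 to 22.5 | 12% to 79% |
| 50% | 75% to 25% | 50% vs 37.5% to 12.5% | 12.5 to 37.5 | 22% to 98% |

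In patient counts, a true rate of 40% with half captured when unprompted gives 45 × 0.40 = 18 against 9, that is 18/45 versus 9/45. The uncorrected χ² has z = 0.20/√(2 × 0.30 × 0.70/45) = 0.20/0.0966 = 2.07, so p = 0.038. Fisher's exact test gives p = 0.065. Data Analysis allows either test for categorical outcomes.

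**Both arms scored.** General symptoms then show no spurious difference from prompting. No figure can be put on the unprompted effects, because the plan gives neither their frequency nor the way they would be recorded.

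**The headache item.** Every patient enters with headache, at a pain score of 5 or more under Study Design, Subjects. No baseline SERSDA is stated. A positive headache item after dosing therefore cannot, on its own, separate an adverse effect from the condition being treated.

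**The case against.** The strongest reply is that the plan is silent rather than wrong. The opening phrase on ketamine explains why the scales were chosen and does not confine them to one arm. Since the objective is a comparison between drugs, at one emergency department, scoring both arms is at least as natural a reading. Several SERSDA items are general symptoms. The exclusions lower the risk of bleeding and hypersensitivity, and follow-up lasts 120 minutes, so such events may be too few among 45 per arm to change a comparison.

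Much of this stands. A reader might infer three stronger claims that the documents do not support:

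- **That aspirin and rimegepant effects are left to spontaneous report.** The plan gives no method at all for other effects. The eligibility condition on describing adverse effects is compatible with direct questioning.
- **That the scales are for Group I only.** This is one possible reading and is nowhere stated.
- **That the recorded rate would be mainly a rate of ketamine-type effects.** The general items contradict this, and the plan never defines the rate as a SERSDA or RASS result.

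Nor is a net direction of bias shown. Scoring Group I alone would raise AOK's rate, whereas missing aspirin effects would lower it.

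The reply does not remove the gap. No sentence secures the same questions in both arms at the same times, and none says which events are counted. Even on the favourable reading, the effects in the last row of the first table have no prompt.

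**Conclusion.** The point holds as a limited one. The plan compares side-effect rates between arms without ensuring symmetric ascertainment. Its only named instruments are introduced for ketamine, their use in both arms and their timing are not stated, and apart from the general SERSDA items nothing prompts for aspirin- or rimegepant-type effects.

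The size is unknown. The 7.5 to 22.5 point range at a 30% true rate, with its 12% to 79% chance of nominal significance, rests on assumed symptom and capture rates and applies only if Group I alone is scored. If both arms are scored, that distortion disappears and what remains is incomplete coverage of unquantified size.

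The change should be made before enrolment because it is cheap and the defect cannot be corrected afterwards. It concerns a secondary outcome and does not threaten the primary analysis.

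**What to change.** Amend the Adverse Events section and the data sheet as follows:

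1. State that SERSDA and RASS are administered to every patient in both arms, at the same post-dose times as the NRS.
2. Add one short fixed checklist of non-ketamine effects (for example abdominal pain or dyspepsia, vomiting, bleeding, rash or other hypersensitivity) and one open question, asked identically in both arms at those times.
3. State which events count towards the adverse-effect rate that is compared between arms.
4. Report SERSDA and RASS results as a separate outcome.
5. Do not count the SERSDA headache item as an adverse effect unless it is compared with a baseline rating.

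The exact checklist is a matter of choice; what matters is that it is common to both arms and fixed in advance. The cost is some protocol wording, a few lines on the data sheet and about a minute more per assessment, at contacts already needed for the NRS. Recorded rates will be higher in both arms. Treatment and sample size are unaffected.

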Data Collection Procedures: Each patient will be approached by a study investigator for acquisition of written informed consent and Health Insurance Portability and Accountability Act authorization after being evaluated by the treating emergency physician and determined to meet study eligibility criteria. When English will not be the participant's primary language, a language-appropriate consent form will be used and non-investigator, hospital-employed, trained interpreters or licensed telephone interpreter will assist in acquisition of informed consent. Baseline pain score will be determined with an 11-point numeric rating scale (0 to 10), described to the patient as "no pain" being 0 and "the worst pain imaginable" being 10. A study investigator will record the patient's body weight and baseline vital signs. All data will be recorded on data collection sheets, including patients' sex, demographics, medical history, and vital signs, and entered into SPSS (version 24.0; IBM Corp) by the research manager. Confirmation of written consent acquisition for all participants, and statistical analyses will be conducted by the statistician, who will work independently of any data collection.

Data Analysis: Data analyses will include frequency distributions and independent-sample t-test to assess differences in pain scores at the various intervals. Mixed-model linear regression will be used to compare changes in pain numeric rating scale across time points. For categorical outcomes (eg, complete resolution of pain), a χ^2 or Fisher's exact test will be used to compare outcomes at 60 and 120 minutes. Based on the validation of a verbally administered rating scale of acute pain in the ED and the comparison of verbal and visual pain scales, we will use a primary outcome consisting of a minimal clinically meaningful difference of 2 points between two groups at the 60-minute and 120-minute pain assessment.^{28,29}

Sample Size: Assuming the minimum statistically significant difference of 2 points on NRS, with Standard deviation of 3.0, alpha=0.05, and power of 80%, the sample size will require 40 patients per group. To account for potential loss to follow up (discharge from the ED before 120 minutes), we will enroll 45 patients in each group.

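### SERSDA includes headache, the entry condition, but has no pre-dose score and no new-or-worse rule, so presenting symptoms can be counted as adverse effects

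*Combined protocol and SAP*

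**What the plan says.** All references are to the combined protocol and SAP.

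- **Who enters.** Under Study Design, patients have acute headache "and an initial pain score of 5 or more on a standard" 0 to 10 scale. The Eligibility Criteria word the threshold slightly differently, but headache is present in every patient either way.
- **What is measured.** The Adverse Events section brings in SERSDA and RASS for ketamine-type effects. On content: "SERSDA Scale includes fatigue, dizziness, nausea, headache, feeling of unreality, changes in hearing, mood change, general discomfort, and hallucinations". Patients grade each item from 0 to 4, with 0 "representing the absence of any adverse effects".
- **What it feeds.** Expected Outcomes: "The secondary outcomes will include a need for rescue analgesia, rates of adverse effects, and change in pain score up to 120 minutes". Side-effect rates are also part of the Study Objectives.
- **What is taken before dosing.** Data Collection Procedures lists a baseline pain score, and then: "A study investigator will record the patient's body weight and baseline vital signs". Sex, demographics and medical history are also recorded. SERSDA is not on the list.
- **How categorical outcomes are compared.** Under Data Analysis, a chi-square or Fisher's exact test "will be used to compare outcomes at 60 and 120 minutes".

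The plan does not say when SERSDA is taken, how nine graded items become a rate, or whether an item must be new or worse after dosing. It also does not say that SERSDA is the only source of adverse-effect data.

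**The concern.** One of the nine items is the condition being treated. Nausea, dizziness, fatigue and general discomfort can also belong to the presenting episode. Without a pre-dose score, a grade above 0 after dosing may be a drug effect, a symptom that was there all along, or a headache that the drug did not relieve.

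Two distortions follow if such grades are counted:

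1. **Dilution.** If the same share of each arm still has headache, both rates rise and a true difference shrinks. The arms then look more alike on safety than they are.
2. **Efficacy read as safety.** If one arm relieves headache less well, more of its patients grade the item above 0, and that arm looks less safe.

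Randomization balances symptoms before dosing on average. It does not prevent dilution, and it does not touch the second distortion, which arises after dosing. The trial is also open-label, so how patients attribute a symptom may differ by arm.

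**Working it through.** **No plan figure to reproduce.** The documents give no adverse-effect rate. The Sample Size section (40 per group, 45 enrolled) is built on the pain score and is not at issue here; it supplies only the group size.

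**Model.** The plan states no rule for combining items, so assume that a patient counts as having a side effect when any item is graded above 0. Let p be the true side-effect rate in an arm, and h the share still grading headache at 1 or more, independent of other effects. Then

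observed rate = 1 − (1 − p)(1 − h).

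When h is the same in both arms, observed gap = (p₁ − p₂)(1 − h).

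**Power.** Two proportions, two-sided 0.05, n = 45 per group, pooled variance under the null (p₁ and p₂ are now the observed rates and p̄ is their mean):

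power = Φ{ [ |p₁ − p₂| − 1.96 √(2 p̄(1 − p̄)/n) ] / √[(p₁(1 − p₁) + p₂(1 − p₂))/n] }

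*Worked line:* p = 0.60 vs 0.20 and h = 0.30.
- Observed rates: 1 − 0.40 × 0.70 = 0.72 and 1 − 0.80 × 0.70 = 0.44; gap 0.28; p̄ = 0.58.
- Null standard error: √(2 × 0.58 × 0.42/45) = 0.1041, and 1.96 × 0.1041 = 0.204.
- Alternative standard error: √((0.2016 + 0.2464)/45) = 0.0998.
- Power = Φ((0.28 − 0.204)/0.0998) = Φ(0.76) = 78%.

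**Dilution, equal h in both arms:**

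| h | True 60% vs 20%: observed | Gap (points) | Power | True 40% vs 20%: observed | Gap (points) | Power |
|---|---|---|---|---|---|---|
| 0 | 60 vs 20% | 40 | 98% | 40 vs 20% | 20 | 54% |
| 10% | 64 vs 28% | 36 | 94% | 46 vs 28% | 18 | 42% |
| 30% | 72 vs 44% | 28 | 78% | 58 vs 44% | 14 | 26% |
| 50% | 80 vs 60% | 20 | 54% | 70 vs 60% | 10 | 17% |
| 70% | 88 vs 76% | 12 | 31% | 82 vs 76% | 6 | 10% |

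With 40 per group and 60% vs 20%, power is 97, 73, 50 and 28% at h = 0, 30, 50 and 70%.

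**False gap, equal true rates of 20% but unequal residual headache:**

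| Residual headache | Observed rates | False gap | Chance of p < 0.05 (formula above) | Fisher's exact |
|---|---|---|---|---|
| 40% vs 60% | 1 − 0.8 × 0.6 = 52%; 1 − 0.8 × 0.4 = 68% | 16 points | about 34% | about 27% |
| 30% vs 60% | 1 − 0.8 × 0.7 = 44%; 1 − 0.8 × 0.4 = 68% | 24 points | about 63% | about 54% |

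All values of p and h are assumptions.

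**The case against.** The strongest reply is that the plan never says it will use an any-item rate. If items are reported one by one, the dilution formula does not apply to the eight items other than headache, and a reader can set the headache line aside. Attribution is also partly built in: the anchors speak of adverse effects and a bothersome side effect, and the Eligibility Criteria require patients to be able to describe side effects as well as rate their pain, which treats the two as distinct. That makes residual-headache shares of 50 to 70% less likely. The false-gap cases need residual headache to differ by 20 or 30 points, whereas the Hypothesis expects similar analgesia. The trial was not sized for side-effect rates, so power for 40% vs 20% is only 54% with no contamination at all. Feeling of unreality and hallucinations, the items closest to the scale's stated purpose, are little affected.

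Much of this stands, and it limits the weight that the power figures can bear. It does not close the gap. An anchor and an eligibility test of ability are not a counting rule, and the plan gives patients no instruction to leave their original headache out. Reporting by item would help, but it is not specified, and without a pre-dose score it still cannot separate existing nausea, dizziness, fatigue or discomfort from a drug effect. Equal pain relief removes the false gap but leaves the dilution.

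**Conclusion.** The concern holds. As written, the plan allows pre-existing or unrelieved symptoms to enter the adverse-effect comparison, and nothing in it would let an analyst remove them afterwards.

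The absence of a pre-dose SERSDA, of assessment times and of a new-or-worse rule is plain from the text. The size is not known: it depends on assumed true rates, an assumed any-item rule, and residual headache that is independent of other effects. Under those assumptions the loss is small at 10% residual headache and substantial from about 30%. Using Fisher's exact test lowers the false-gap figures but does not change the conclusion.

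The problem is confined to a secondary outcome, and the primary pain comparison is untouched. It should be corrected because the correction is cheap and cannot be made after the data are collected.

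**What to change.** 1. Record SERSDA once before dosing and again with the post-dose pain assessments at 60 and 120 minutes.
2. Count a side effect only when an item is new or its grade is higher than at baseline.
3. Report each item separately by arm.
4. Show the headache item on its own line, including worsening from baseline, and give the any-side-effect rate without it.
5. State these rules, and any other source of adverse-effect data, before analysis.

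A baseline RASS is optional, since patients must already be awake and alert to enter.

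**Cost.** One nine-item questionnaire before dosing and a few lines of analysis text; no extra patients.

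**Downsides.**
- The resulting rate is not directly comparable with unmodified SERSDA totals, though those can be reported alongside.
- An item already at grade 4 before dosing cannot show worsening.
- Other symptoms that worsen because the headache itself worsens will still count.
- Worsening headache leaves the summary rate, so its separate line must not be omitted.

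### No pre-dose side-effect score is specified and no rule limits adverse effects to new or worsened symptoms, so symptoms present on arrival may be counted, biasing the comparison in a direction that depends on how each drug relieves them

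*Combined protocol and SAP*

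**What the plan says.** Comparing side-effect rates is part of the Study Objectives. Under Expected Outcomes the secondary outcomes are "a need for rescue analgesia, rates of adverse effects, and change in pain score up to 120 minutes".

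The Adverse Events section names two instruments, SERSDA and RASS. On content, "SERSDA Scale includes fatigue, dizziness, nausea, headache, feeling of unreality, changes in hearing, mood change, general discomfort, and hallucinations". Patients grade each item on five points, "with “0” representing the absence of any adverse effects and “4” representing a severely bothersome side effect". The section gives no assessment times for either scale, no score that qualifies as an adverse effect, and no rule for a symptom already present before dosing.

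Data Collection Procedures names the baseline pain score and then states: "A study investigator will record the patient's body weight and baseline vital signs". The data sheets also hold sex, demographics, medical history and vital signs. SERSDA and RASS are not mentioned there. Under Data Analysis, for categorical outcomes a χ² or "Fisher's exact test will be used to compare outcomes at 60 and 120 minutes", with no baseline adjustment described.

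Patients enter with acute headache and, under Study Design, "an initial pain score of 5 or more on a standard 11- point (0 to 10) numeric rating scale". The Introduction says of benign ED headaches that they are, for the most part, primary headache disorders: "90% of these headaches classified as tension, migraine, or cluster".

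**The concern.** Pain is measured before dosing and analysed as change over time. The side-effect scale gets neither, although its items overlap with what a headache patient may bring to the ED. The exclusion criteria do not remove patients with nausea, dizziness, fatigue or general discomfort.

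Without a pre-dose score, a non-zero item after dosing has three possible meanings: a drug effect, a symptom that was there already, or a symptom that was worse on arrival and is improving. The scale's anchors label all three as side effects, and the plan has no rule that separates them. The reported rates could then not be read as drug effects. The contrast between arms would depend partly on how well each drug relieves presenting symptoms, which is a question of efficacy. Treatment-emergent status cannot be reliably recovered afterwards if no pre-dose score exists.

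**Working it through.** **Inputs.** The documents give no adverse-effect rate, no prevalence of symptoms on arrival and no power for this outcome, so there is no plan figure to reproduce. The trial is sized on pain only (Sample Size section). The one input taken from the plan is the enrolled number, 45 per arm. Everything else below is an assumption:

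- true new-onset rates for any non-headache SERSDA item: q₁ = 50%, q₂ = 20% (difference 30 points);
- share of patients with such a symptom on arrival, all of it persisting to the assessment: b = 20%, 40% or 60%;
- any non-zero score counts as an adverse effect, and arrival symptoms are independent of new onset.

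**Step 1: equal, full persistence.** A patient is a case if an arrival symptom persists or a new one appears:

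observed rate = b + (1 − b)q, so observed difference = (1 − b)(q₁ − q₂).

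Power is from exact enumeration of the uncorrected χ² test, two-sided 5%, 45 per arm.

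| b | Arm with q₁ = 50% | Arm with q₂ = 20% | Difference | Power |
|---|---|---|---|---|
| 0 | 50% | 20% | 30 points | 0.87 |
| 20% | 60% | 36% | 24 points | 0.62 |
| 40% | 70% | 52% | 18 points | 0.42 |
| 60% | 80% | 68% | 12 points | 0.26 |

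The shrinkage arises from overlap. A patient who already counts as a case cannot become one again through a drug effect, and this hides more true events in the arm that has more of them. At b = 40% the first arm gains 20 points (50% to 70%) and the second gains 32 (20% to 52%). Had both arms gained the same amount, the difference would not have moved.

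**Step 2: unequal persistence.** Let b now be the share symptomatic on arrival and r the probability that the symptom persists in a given arm:

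observed rate = q + (1 − q) × b × r.

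With b = 40%:

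- r = 90% vs 30%: 0.50 + 0.50 × 0.40 × 0.90 = 0.68, and 0.20 + 0.80 × 0.40 × 0.30 = 0.296. Difference 38 points, wider than the true 30.
- r = 30% vs 90%: 0.50 + 0.50 × 0.40 × 0.30 = 0.56, and 0.20 + 0.80 × 0.40 × 0.90 = 0.488. Difference 7 points.
- r = 50% in both arms: 0.60 and 0.36. Difference 24 points.
- r = 0 in both arms: 0.50 and 0.20. No bias.

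With b = 60% and r = 30% vs 90%: 0.50 + 0.50 × 0.60 × 0.30 = 0.59, and 0.20 + 0.80 × 0.60 × 0.90 = 0.632. The difference is −4 points, so the order of the arms reverses.

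**Step 3: what carries over.** The factor (1 − b) applies whenever persistence is equal, with b read as the share whose arrival symptom persists. Once persistence differs by arm, the sign of the bias is not determined.

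**The case against.** The strongest reply is that the plan is silent and not wrong. It gives no SERSDA schedule at all, and the list of data-sheet contents is introduced as inclusive, so it need not be complete. A reader might infer that SERSDA is never given before dosing. The text does not say so; it only fails to specify it. A reader might also infer that every arrival symptom will be counted as a drug effect. No counting rule is written either way, and because the anchors speak of side effects, a patient who arrived nauseated could reasonably score 0. Eligible patients must also be able to describe their adverse effects. This is fair as a limit on what can be claimed. It does not protect the comparison: self-attribution is imperfect, more so in an open-label trial, and the plan does not rely on it explicitly.

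Second, a difference biased toward zero, making the products look falsely alike, is tempting as a general conclusion. Step 2 shows that it requires similar persistence in both arms. Since both drugs are given to relieve headache, equal relief of accompanying symptoms cannot be presumed.

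Third, the prevalence and rate inputs have no source in the documents, the any-item endpoint is not one the plan defines, and the outcome is secondary. All of that stands. SERSDA was chosen for effects particular to ketamine, and hallucinations and feeling of unreality are probably uncommon on arrival (an assumption), so item-level comparisons of those would be less affected.

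Fourth, RASS is less exposed, because eligibility already requires patients to be alert and oriented and excludes altered mental status.

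**Conclusion.** The point holds as a gap in specification with a real consequence. No pre-dose SERSDA is specified, and nothing confines adverse effects to new or worsened symptoms. On the scale's anchors, arrival symptoms may be counted, and the adverse-effect comparison, which is both a stated objective and a secondary outcome, would then not separate them from drug effects.

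The direction of bias is conditional: toward zero under equal persistence, either way or reversed under unequal relief. The size is unknown. The ranges shown (12 to 24 points under full persistence; 7 or 38 points under unequal persistence at 40% prevalence; a true difference of 30 throughout) illustrate the mechanism and are not estimates for this trial.

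The primary pain outcome is unaffected. The change is worth making before enrolment because the missing score cannot be obtained later. The point does not depend on the headache item, although that is the plainest overlap: every patient has a headache at entry, so that item partly measures residual pain.

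**What to change.** State the SERSDA schedule: once before dosing in both arms, together with the baseline NRS, and again at the 60- and 120-minute assessments. Define an adverse effect as an item whose post-dose score exceeds that patient's own pre-dose score, and report rates and worst severity by arm on that definition. A pre-dose RASS is optional.

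The cost is a short protocol addition and one nine-item questionnaire per patient, at a point where baseline pain is already being asked: about two more minutes before dosing (an estimate), with no extra patients or staff. Reported adverse-effect counts will be lower than raw non-zero scores would give, and the report should say so.
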